8.3 Study procedures

8.3.1 Visit 1: Screening visit and informed consent

The screening visit will take place at the NUTRIM Clinical Research Unit (CRU) of Maastricht University. At this first visit, all participants will be asked to confirm that they have read the information letter, received oral information, and have no further questions regarding the study. The investigator will ensure the participant understands all the information through an interview. Afterward, the eligibility criteria will be checked, and if suitable, the participant will be asked to complete written informed consent prior to any study procedures. Following inclusion, the medical history of each participant will be checked during a structured interview and participants will be requested to complete several questionnaires, including a baseline characteristics questionnaire

(F1.1_Baseline_Characteristics_Questionnaire_Versie2.0_dd 26-03-2025), GAD-7 (F1.2_GAD7_Versie1.0_dd 10-10-2024), PHQ-9 (F1.3_PHQ9_Versie1.0_dd 10-10-2024)), and BFI (F1.4_BFI_Versie1.0_dd 10-10-2024), with the support of Castor EDC. Given that current or lifetime psychopathology serves as an exclusion criterion and the GAD-7 and PHQ-9 assess for the presence of anxiety and depression disorders, respectively, participants scoring 10 or above on either questionnaire will be excluded from the study (50).

8.3.2 Visit 2: Test day

Participants will arrive at the NUTRIM CRU at Maastricht University after an overnight fast. To account for the distinct circadian rhythms of the hormones being measured, the test day is scheduled between 9:00 a.m. and 12:00 p.m. This timing ensures that measurements are taken before the natural ghrelin peak, which typically occurs around noon, optimizing sensitivity to detect any effects of the intervention (61, 62). Although cortisol levels peak around 8:00 a.m. and are still in decline during this window, they are not yet at their most stable (62). However, this is deemed acceptable since cortisol is a secondary outcome. Additionally, this time frame helps minimize the required fasting duration for participants, enhancing both feasibility and comfort.

Upon arrival, all participants will complete a checklist to verify compliance with the test day regulations. These regulations include not eating for at least 6 hours before the test day and not consuming extremely spicy or fatty foods, as well as alcohol, on the day prior to the test day. On the day of the test, participants are only permitted to drink small amounts of water. Additionally, due to the cortisol sampling, participants must refrain from consuming caffeine or engaging in physical exertion on the day of the test day. Participants should also avoid brushing their teeth, chewing gum, or smoking for at least 1 hour before the test session begins.

Once compliance is confirmed, the coordinating investigator will prepare the tVNS device to ensure it is ready for immediate use after nausea induction. This preparation involves adjusting the stimulation current based on each participant's sensitivity, keeping it below the sensory threshold, with current intensities ranging from 0.25 to 10mA.

Following this, the investigator will place an intravenous cannula for blood collection to measure plasma levels of ghrelin and motilin at four different time points.

Thereafter, the investigator will manually insert a nasogastric tube (Nutricair Enteral-Enfit, Charrière 10) to facilitate intragastric infusion of a 50% fat emulsion (Calogen, NUTRICIA, Netherlands) in water (see D6.1_SPC_Calogen_Versie1.0_dd 16-10-2024 & F4.1_Nasogastric_Tube_Placement_SOP_Versie1.0_dd 14-10-2024). The fat emulsion consists of 50% long-chain triglycerides and 50% water. The infusion will be administered at a rate of 5 ml/min (22.5 kcal/min) using an Applix Smart pump and a Nutricair Enteral-Enfit syringe, following methodologies used in previous research that successfully induced nausea (1). Based on a prior study, we expect that a mean

volume of 258 ± 32 ml will be necessary to induce nausea (1). Participants will be closely monitored throughout the infusion for the onset of nausea, with assessments every 5 minutes using a 0-100 Visual Analogue Scale (VAS) to record their symptoms. If a predetermined VAS score of 50/100 is reached, or when the participant starts retching, the lipid infusion will be promptly halted to prevent excessive discomfort. Participants will explicitly be informed about the predetermined 50/100 threshold on the VAS scale, but also the maximum time limit for the infusion, and the possibility of being considered a drop-out if the nausea score does not reach 50/100.

Participants will also be informed in advance about how to use the VAS scale and how to indicate their nausea score. Concrete examples will be discussed, such as: "If you don't feel nauseous at all, mark 0 on the scale," "If you feel slightly nauseous but can still function normally, give a score of 30 or 40," "If you feel clearly nauseous and uncomfortable, but can still function normally, give a score of 50," "If you feel very nauseous, for example, if you are about to vomit, give a score of 80 or higher." This is based on progressive intensity scores that were defined as follows: 0, absent sensation; 10 and 20, faint sensation; 30 and 40, mild sensation; 50 moderate sensation; 60 and 70, strong sensation, and 80, imminent vomiting sensation (1).

Throughout the procedure, participants will be closely monitored for the severity of nausea. To ensure safety, the VAS will be administered at regular 5-minute intervals. Furthermore, participants will be asked to notify the research team if a VAS score of 50/100 (or higher) is reached between scheduled assessments, allowing the infusion to be stopped earlier if necessary.

The lipid infusion will be immediately halted if the participant's nausea score reaches the 50/100 threshold or if they begin retching. This is to prevent excessive discomfort. Any signs of severe nausea, such as vomiting or a participant's request to stop the procedure, will also lead to immediate cessation of the infusion.

After stopping the infusion, the nasogastric tube will be promptly removed, and participants will then receive either taVNS or sham stimulation for 30 minutes. During this stimulation phase, the severity of nausea will be assessed using a 0-100 VAS score, where 0 signifies "no nausea" and 100 represents "the worst nausea imaginable". VAS scores will be recorded every 5 minutes, continuing for 30 minutes post-stimulation to evaluate the efficacy of taVNS in alleviating nausea. VAS scores

for other gastrointestinal symptoms will also be recorded at the same time points as nausea severity. Additionally, VAS scores for the desire to eat will be recorded at four specific time intervals.

Plasma levels of ghrelin and motilin and salivary cortisol will be measured on four different time points: baseline, at the end of nausea induction, immediately after the taVNS vs. sham stimulation, and 60-minutes post-nausea induction.

Autonomic parameters, including heart rate variability and skin conductance, will be continuously recorded from the onset of nausea induction until 30 minutes after either taVNS or sham stimulation. These measurements will be captured using a Shimmer3 GSR sensor and Fitbit smartwatch, as was previously utilized in other studies within our department (NL87188.068.24/METC 24-029). The Shimmer3 GSR sensor, a CE-certified device (see K6.6_Shimmer_CE_Certificate_of_conformity_Versie1.0_dd 04-09-2014) will be used to collect data on heart rate variability and skin conductance. The Fitbit wearable device will be used to collect participant data concerning HRV. The device will be connected to the coordinating investigator's smartphone via Bluetooth and the Fitbit app. Heart rate data will then be automatically collected by the Fitbit.

Once all measurements are completed, the tVNS device, intravenous cannula, Shimmer, and Fitbit will be removed.

The investigators will ensure that participants are in stable condition before they leave Maastricht University. Since nausea is influenced by gastric distension and chemical signals, its resolution likely follows the reduction of these factors. After stopping the fat infusion, gradual gastric emptying reduces mechanical stimulation. Due to slow fat digestion, nausea is expected to subside gradually, with acute distension resolving first, though mild residual symptoms may persist. If the VAS score falls below 50/100 after stimulation (expected within 30-60 minutes), participants are assessed for fitness to leave based on subjective well-being and symptom resolution. They must function independently without severe nausea (e.g., vomiting, disorientation). If still above 50/100, monitoring continues every 5 minutes for safety until nausea sufficiently declines.

Finally, participants will be asked to fill out a reimbursement form. Contact numbers of the investigators and the emergency department will be provided for any issues that arise within 24 hours after the test.

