Participants will arrive at the NUTRIM CRU at Maastricht University after an overnight fast. Compliance with test day regulations will be checked (e.g. fasting, no alcohol). Once compliance is confirmed, the coordinating investigator will properly set up the tVNS device to ensure it can be used immediately after nausea induction. This setup includes adjusting the stimulation current of the tVNS device according to each participant's sensitivity, ensuring it remains below the sensitivity threshold, with current intensities ranging from 0.25 to 10 mA. This is important because active stimulation will be programmed to deliver only subthreshold stimuli. Next, an intravenous cannula will be placed for blood collection. Thereafter, the

investigator (a medical doctor) will manually place a nasogastric tube to facilitate the intragastric infusion of a 50% fat emulsion in water. This method of infusion is selected to replicate the conditions under which dietary fat is ingested as part of a meal. The infusion will be administered at a rate of 5 ml/min, consistent with previous research in which nausea was induced through similar methodologies (1). Participants will be closely monitored throughout the infusion for the onset of nausea, with assessments every 5 minutes using a 0-100 Visual Analogue Scale (VAS) to quantify the nausea severity. Participants will receive clear instructions on how to rate their nausea and indicate its intensity. If a predetermined VAS score of 50/100 is reached, or should the participant start retching, the lipid infusion will be promptly halted to prevent excessive discomfort. Participants will be informed in advance about the 50/100 VAS threshold and provided with guidance on how to interpret and apply this rating. Following the cessation of the infusion, the nasogastric tube will be removed for patient comfort, after which either taVNS or sham stimulation will be administered for 30 minutes.

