A duration of 30 minutes was selected based on the mechanism of action of taVNS, which is assumed to act via the activation of the nucleus of the solitary tract (NTS) in the brainstem. Furthermore, this choice is also consistent with other studies on taVNS conducted within our department (NL87188.068.24/METC 24-029). The NTS serves as the primary relay station for vagal input and plays a critical role in modulating autonomic functions. In a previous study by Frangos et al. (24), NTS activity gradually decreased during stimulation but peaked shortly after the cessation of a 7-min stimulation of the cymba conchae. Furthermore, other brain regions exhibited a gradual increase in activity during stimulation, reaching their peak during the post-stimulation phase, with this heightened activity persisting for up to 11 minutes. Hence, a stimulation period of 30 minutes is expected to provide an optimal timeframe for taVNS to exert its maximum effect and to counterbalance the effects of nausea.

Both the taVNS treatment and sham stimulation will be administered using a tVNS device that provides stimulation to the cymba conchae of the left ear. The left side is chosen due to the innervation pattern of the left vagus nerve, which predominantly innervates the stomach and the pyloric area (25, 26). This choice aligns with our ultimate clinical interest in conditions such as gastroparesis and functional dyspepsia. Additionally, it ensures comparability with other studies conducted within our department, including the “tVNS and GI motility” study (NL86446.068.24).

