5.1 Investigational product/treatment

The intervention of interest is taVNS, with sham stimulation employed as the appropriate control.

5.1.1 taVNS

Electrical stimulation will be administered to the auricular branch of the vagus nerve, specifically at the cymba conchae of the left ear, using a custom-made device called tVNS R (tVNS Health GmbH, Grünwald, Germany). This device has previously been used in the RESILIENCE study (NL84720.068.23/METC 23-032) and comprises a stimulation unit and an ear electrode. This electrode is connected as an anode to the stimulation device by a cable and is worn similarly to an earphone. The stimulation unit sends electrical impulses through the electrode, which stimulates the auricular branch of the vagus nerve. On the test day, subjects assigned to the taVNS group will receive 30 minutes of active stimulation after the nausea induction. According to recent systematic analyses determining the most optimal treatment frequencies for taVNS, the stimulation parameters will consist of biphasic rectangular pulse trains with an impulse frequency of 25Hz, impulse duration of 30 seconds, followed by an impulse pause of 30 seconds, and an impulse width of 450ms (27, 28). Each participant will undergo sensory testing prior to the commencement of the treatment period during which the current will be adjusted to suprathreshold stimulation intensity, with current intensities ranging between 0.25 and 10 mA. The device will indicate stimulation delivery by blinking.

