5.1.2 Sham stimulation

In the control group, sham stimulation will be administered to the same electrode location (left cymba conchae) using an identical device as that used for taVNS. The electrode used for sham stimulation will be non-conducting, ensuring that there is no stimulation of the vagus nerve. Although the devices for tVNS and sham stimulation appear identical, the electrodes for each group are slightly different. Consequently, the investigator responsible for programming the devices will be aware of the treatment allocation. Participants will not be aware of the treatment received since stimulation is provided to the same location, and the device will still blink during both types of stimulation to maintain blinding (28). The randomization code will be altered

before analysis, ensuring that the investigator conducting the data analysis remains unaware of the treatment allocation. The randomization code will be kept confidential until after the modified intention-to-treat analysis has been reported.

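### The stated test-day order puts current calibration before the cannula, so baseline ghrelin and motilin may be post-stimulation and may differ by arm

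*Protocol*

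**What the plan says.** Protocol sections 3 and 8.3.2 give the test day in the same sequence: compliance check, device set-up, cannula, nasogastric tube, lipid infusion, then 30 minutes of active or sham stimulation.

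- **Device step (8.3.2):** "This preparation involves adjusting the stimulation current based on each participant's sensitivity, keeping it below the sensory threshold".
- **Next step (8.3.2):** "Following this, the investigator will place an intravenous cannula for blood collection", which the same sentence ties to all four ghrelin and motilin samples. Section 3 has the same order: "Next, an intravenous cannula will be placed for blood collection".
- **Sampling times (8.3.2):** "Plasma levels of ghrelin and motilin and salivary cortisol will be measured on four different time points: baseline, at the end of nausea induction", followed by samples after stimulation and 60 minutes after induction. Section 8.3.3 repeats these times. Neither section places baseline relative to calibration.
- **Who is calibrated (5.1.1, the taVNS subsection):** "Each participant will undergo sensory testing prior to the commencement of the treatment period during which the current will be adjusted".
- **Sham electrode (5.1.2):** it is non-conducting, "ensuring that there is no stimulation of the vagus nerve".
- **Allocation (8.2):** participants are randomised before the test day, and the investigator who programs the device knows the allocation.

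**The concern.** A baseline used to judge a treatment effect should be taken before any exposure to the treatment. Setting a current to someone's sensitivity means passing current through the ear, at the site and with the device used for treatment. In the written order this happens before blood can be drawn through the cannula.

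Secondary objective 3 asks whether induction lowers ghrelin and motilin and whether taVNS counteracts the fall. Section 8.1.2 describes these endpoints as changes in level, and section 10.2 applies the mixed model of section 10.1, which allows baseline adjustment if needed. If the first sample already carries an effect of stimulation in one arm and not the other, a contrast against that sample mixes the calibration effect with the treatment effect. The first sample is also the only one taken before induction, so the induction part of the hypothesis has no other reference.

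**Working it through.** The plan gives no figure on this point, so the check is of sequence and then of what each possible reading implies.

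**Step 1: does baseline blood follow calibration?** Section 3 puts device set-up before the cannula, and so does 8.3.2. Section 8.3.2 says the cannula serves all four ghrelin and motilin samples, and baseline is the first of them. As written, baseline blood follows calibration.

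**Step 2: who has received current by then?** The protocol does not say which electrode is used to calibrate a sham participant. There are two readings.

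- *Assigned electrode, or no real calibration in sham.* Active participants receive current before baseline; sham participants do not.
- *A conducting electrode for everyone.* Both arms receive current before baseline. Exposure is balanced, but the sample is pre-stimulation in neither arm.

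On both readings the active arm's first blood sample is taken after current. They differ only on whether the arms differ.

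**Step 3: what does that do to the comparison?** Let D be the true between-arm difference at a later sample, and let cA and cS be the shifts in the baseline sample caused by calibration in the active and sham arms.

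- Expected difference in change from baseline = D − (cA − cS).
- With baseline as a covariate with slope b: approximately D − b × (cA − cS).
- Conducting electrode in everyone: cA = cS on average, so the bias is zero.
- Assigned electrode: cS = 0, so the bias is cA (or b × cA). It understates D if cA has the same sign as D, and overstates D if the signs are opposite.
- If stimulation does not move these hormones, cA = 0 and any baseline imbalance is chance.

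**Step 4: can cA be sized?** No. It would need the length of calibration, the interval to the draw, and the hormone response to a short exposure, none of which is given. The nearest figure is in section 3, on brain activity after a 7-minute stimulation: "with this heightened activity persisting for up to 11 minutes". That concerns brain regions, not ghrelin or motilin, and a longer exposure than a threshold search need be.

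**Step 5: is there another reference before treatment?** Yes, the sample at the end of induction. Section 5.2.1 expects 258 ml at 5 ml/min, and 258 / 5 = 51.6 minutes, which agrees with its stated 52 ± 6 minutes. At that expected duration the sample comes more than 11 minutes after calibration, so a short-lived shift would probably have faded. This rests on the expected duration; the protocol sets a maximum of 1.5 hours but no minimum.

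**The case against.** The strongest reply is that differential exposure is not in the text. Sections 3, 5.1.1 and 8.3.2 speak of each participant, and a non-conducting electrode cannot reveal a sensory threshold. Taken literally, everyone is tested with a conducting electrode and the arms are balanced. The statement in 5.1.2 about no vagal stimulation describes the sham treatment, not calibration. This stands: a reader might infer that only the active arm receives current before baseline, but the protocol does not establish it. What remains is that the protocol leaves the matter open, and that on the balanced reading the first sample is still not pre-stimulation.

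A reader might also infer that the cortisol baseline is late. It is not shown to be: saliva needs no cannula and its place in the order is unstated. The same holds for the VAS baseline, which 8.3.4 fixes only as before the infusion. Figure 1 and the sampling procedures cited in 8.3.3 are not available here and may settle these timings. They would not alter the order written twice in the protocol for blood, though they might need reconciling with it.

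Third, the stakes are limited. The primary nausea outcome is not shown to be affected. Objective 3 is worded around levels after induction, and the end-of-induction sample offers a reference directly before treatment. This stands for the treatment contrast. It does not supply a pre-induction value for the claim that induction lowers the hormones.

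**Conclusion.** The point holds in limited form. The written sequence makes the baseline ghrelin and motilin sample follow calibration, and the protocol does not say how sham participants are calibrated. That baseline may therefore be post-stimulation and may differ by arm.

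This rests on two assumptions: that baseline blood is drawn through the cannula, as 8.3.2 indicates, and that adjusting current to sensitivity involves delivering some. A reader might go on to infer a definite percentage loss of the hormone effect; the document supports no such figure, and even the direction of any bias is unknown. The consequence is confined to secondary hormone outcomes and softened by the end-of-induction sample. The point is worth making because the defect lies in a stated order and the remedy is simple.

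**What to change.** 1. In sections 3 and 8.3.2, place the cannula and baseline blood draw, together with baseline saliva and baseline VAS scores, before device calibration. Tube placement and infusion then follow.
2. In 8.3.3, define baseline as before any current is delivered and before the nasogastric tube is placed.
3. State how sham participants are calibrated, including which electrode is used, and how long calibration lasts.
4. Reconcile 5.1.1, which sets the current above the sensory threshold, with sections 3 and 8.3.2, which keep it below. The intensity delivered during calibration cannot be described until these agree.

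The cost is wording in the protocol and the related sampling procedures, with notification of the amendment to the ethics committee under 12.3. No procedures, samples or participants are added. If anyone has already been tested in the current order, their baseline samples should be flagged.

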8.3.3 Biological samples

Plasma ghrelin and arginine vasopressin: On the test day, plasma levels of ghrelin and motilin will be measured in response to nausea induction, as these hormones are expected to be influenced by the nausea response (3). Blood samples will be drawn at four predetermined time points: baseline, at the end of nausea induction, immediately after the taVNS vs. sham stimulation, and 60-minutes post-nausea induction. Plasma will be collected in EDTA tubes kept on ice, followed by centrifugation. The samples will then be stored at -80 °C until analysis. For a detailed description of the sample collection and processing procedures, see F4.2_Blood_Samples_SOP_Versie1.0_dd 14-10-2024.

Salivary cortisol: Salivary cortisol levels will be measured in response to nausea induction, as this hormone is expected to elevate due to the stress response triggered by nausea (60). Saliva samples will be collected at four predetermined time points: baseline, at the end of nausea induction, immediately after the taVNS vs. sham stimulation, and 60-minutes post-nausea induction. Saliva samples will be collected using synthetic Salivette devices. The samples will be processed as soon as possible and will be promptly stored at -80 °C until further analysis. The analysis of the samples will be conducted at the end of the study period in the laboratory of Maastricht University using immunoassay (ELISA SLV-2930). See F4.4_Cortisol_Samples_SOP_Versie1.0_dd 2-4-2025 for a detailed description of the saliva cortisol sample collection process and subsequent processing.

